### 3.1.3 Lesions counts on the face and trunk

Inflammatory Lesions will be defined as follows:

**Papule -** A small, red, solid elevation less than 0.5 cm in diameter. **Pustule -** A small, circumscribed elevation of the skin that contains yellow-white exudates.

Non-inflammatory Lesions will be defined as follows:

**Open Comedone -** A pigmented dilated pilosebaceous orifice (blackhead). **Closed Comedone -** A tiny white papule (whitehead).

Note: The truncal lesion counts will not be performed for subjects between 9 and 11 years old who do not have moderate acne on the trunk at Baseline (i.e. who do not have PGA of 3, at least 20 inflammatory lesions on the trunk and at least 20 non-inflammatory lesions on the trunk).

#### 3.1.4 Subject self-assessment of facial acne improvement

Subjects will evaluate by his/her own their facial acne improvement by comparing what they recall on their disease at the start of the study at the Week 12/ET visit according to the following scale:

Subject's Assessment of Acne Scale		
0	Complete Improvement	
1	Marked Improvement	
2	Moderate Improvement	
3	Minimal Improvement	
4	No Change	
5	Worse	

#### 3.2 Safety Assessment

A safety assessment will be conducted for all subjects at the Screening visit (from the time of ICF signature) and every subsequent visit.

The safety parameters are the recording of adverse events, laboratory safety tests, physical examination, vital signs and local tolerability scores (0 [none] to 3 [severe]) for erythema, scaling, dryness, and stinging/burning as specified in sections 7.2.1 to 7.2.5 of the protocol.

Specific requirements for children between 9 and 11 years old who do not have moderate acne on the trunk at Baseline (i.e. do not have PGA of 3, at least 20 inflammatory lesions on the trunk and at least 20 non-inflammatory lesions on the trunk):

If the investigators decide to start the treatment for truncal acne in these subjects during the study, then the local tolerability scales (for trunk) will be completed and data will be evaluated in the safety analysis.

Galderma R&D RD.06.SPR.18252 Page 8 of 25

Local tolerability (erythema, scaling, dryness, and stinging/burning) will be assessed on the face and trunk separately.

## **3.3** Other Assessment

## **3.3.1 Photographs (at selected sites)**

Facial and truncal photographs will be taken as per standardized procedure and guideline at the Baseline, Week 2, 4, 8, and Week 12/ET Visits at selected sites to illustrate the observed effect.

## 3.3.2 Dermatology Life Quality Index (DLQI) / Children's Dermatology Life Quality Index (C-DLQI)

The Dermatology Life Quality Index (DLQI, designed for use in adults, i.e. subjects over the age 16 years old) and Children's Dermatology Life Quality Index (C-DLQI, designed for 16 years or younger at the date of Baseline visit) will be completed at Baseline and Week 12/ET visits.

The DLQI/ C-DLQI will measure the dermatology-related limitations of functional ability and the frequency, severity and impact of acne symptoms on subjects' lives and acne-related quality of life. The six areas (domains) addressed in the questionnaire are: symptoms and feelings; daily activities; leisure; work/school; personal relationships; and treatment. The score on the DLQI/ C-DLQI has a possible range of 0 to 30 and can also be presented as a percentage of the maximum possible score of 30.

# 4 EFFICACY AND SAFETY ENDPOINTS

#### 4.1 Efficacy Endpoints

The imputation of missing data for the efficacy endpoints is described in Section 7.4.2.2.

# 4.1.1 Primary Efficacy Endpoint

The primary efficacy endpoint consists of the following 3 co-primary endpoints:

- 1. Success Rate, defined as the percentage of subjects who achieve an IGA score of 1 (almost clear) or 0 (Clear) and an at least a 2-grade improvement from Baseline at Week 12.
- 2. Absolute Change in facial non-inflammatory lesion count from Baseline to Week 12
- 3. Absolute Change in facial inflammatory lesion count from Baseline to Week 12

Galderma R&D RD.06.SPR.18252 Page 9 of 25

# 4.1.2 Secondary Efficacy Endpoint

The secondary efficacy endpoint consists of the following 3 co-secondary endpoints:

- 1. Percentage of subjects who achieve a PGA score of 1 (almost clear) or 0 (Clear) and an at least 2 grade improvement from Baseline to Week 12.
- 2. Absolute change in truncal non-inflammatory lesion count from Baseline to Week 12
- 3. Absolute change in truncal inflammatory lesion count from Baseline to Week 12

## 4.1.3 Supportive Efficacy Endpoints

- 1. Percent change in facial non-inflammatory lesion counts from Baseline to Week 12.
- 2. Percent change in facial inflammatory lesion counts from Baseline to Week 12.
- 3. Percent change in truncal non-inflammatory lesion counts from Baseline to Week 12.
- 4. Percent change in truncal inflammatory lesion counts from Baseline to Week 12.
- 5. Subjects' assessment of facial acne improvement

#### 4.2 Safety Endpoints

The safety endpoints are the following:

- 1. Treatment-emergent Adverse Events (TEAE): defined as an adverse event that occurred on or after the first study drug application.
- 2. Change from baseline of Local tolerability (Face)
- 3. Change from baseline of Local tolerability (Trunk)
- 4. Change from baseline of Laboratory Safety Test (Hematology, Chemistry, UA)

#### 4.3 Other Endpoints

Other endpoints are the following:

1. Dermatology Life Quality Index (DLQI) / Children's Dermatology Life Quality Index(CDLQI)

#### 5 **POPULATIONS ANALYZED**

The Intention to Treat (ITT) population will be used for all efficacy endpoints on the face. The Intention to Treat on the Trunk (ITTT) population will be used for all efficacy endpoints on the trunk. The Safety population (SAF) will be used for all safety analyses except for the local

Galderma R&D RD.06.SPR.18252 Page 10 of 25

tolerability on the trunk; and the Safety Population on the Trunk (SAFT) will be used for the analysis of local tolerability on the trunk. The Per Protocol (PP) population will be used for supportive analyses of the primary efficacy endpoint on the face; and the Per Protocol Population on the trunk (PPT) will be used for supportive analyses of the secondary efficacy endpoint on the trunk.

In the case that the SAFT turns out to be identical to the SAF population, then all safety analysis will be based on the SAF population.

In the case that the ITTT population turns out to be identical to the ITT population, then all efficacy analyses will be based on the ITT population.

In the case that the PPT population turns out to be identical to the PP population, then the supportive analyses of the primary and secondary efficacy endpoints will be based on the PP population.

# 5.1 Intention to Treat (ITT) Population

The ITT population is defined as any subjects who are randomized. Data from subjects included in the ITT population will be analyzed according to the treatment as randomized.

#### 5.2 Intention to Treat on the Trunk (ITTT) Population

The ITTT population is defined as any subjects in the ITT population with moderate truncal acne at Baseline visit. In practice, this excludes from the ITT population the children between 9 and 11 years old who did not meet inclusion criterion #4 (PGA) or #5 (Truncal lesion counts) at study entry and therefore not planned to be treated on the trunk.

Subjects in the ITTT population will be analyzed according to the treatment as randomized.

## 5.3 Safety (SAF) Population

The SAF population is defined as comprising the ITT population subjects who applied/were administered the study medication at least once.

The SAF population is used for all safety analyses, except for the local tolerability on the trunk.

#### 5.4 Safety (SAFT) Population for Local Tolerability on the Trunk

The SAFT population is defined as the SAF subjects who also applied/were administered the study medication on the trunk at least once.

#### 5.5 Per Protocol (PP) Population

The PP population is defined as comprising the ITT subjects who have no major protocol deviations. The primary efficacy analyses (on the face) will be repeated based on the PP Population to confirm the results.

Galderma R&D RD.06.SPR.18252 Page 11 of 25

Potential major protocol deviations may include but are not limited to:

- 1. Entrance Criterion Deviations:
  - a. Out of range baseline lesion counts
  - b. Out of range baseline IGA grade
  - c. Inclusion/exclusion criterion violation
- 2. Non-Compliance:
  - a. Subjects who have dosing deviations more than 30% of the planned 84 doses
  - b. Subjects who miss doses for 5 or more consecutive days just prior to the last visit
- 3. Prohibited Medications: Subjects who have taken interfering concomitant therapies during treatment
- 4. Administrative error:
  - a. Accidental unblinding
  - b. Medication dispensing errors
  - c. Lesion counts and IGA/PGA performed by a non-approved evaluator

The final list of major protocol deviation criteria and subjects who have any major protocol deviations will be documented in the blind review memo before database lock.

## 5.6 **Per Protocol (PPT) Population on the Trunk**

The PPT population is defined as any subjects in the PP population with moderate truncal acne at the Baseline visit. In practice, this excludes from the PP population the children between 9 and 11 years old who did not meet inclusion criterion #4 (PGA) or #5 (Truncal lesion counts) at study entry (i.e. who do not have PGA of 3, at least 20 inflammatory lesions on the trunk and at least 20 non-inflammatory lesions on the trunk); or subjects who will be deemed not evaluable for the analyses on the trunk.

The secondary efficacy analyses (on the trunk) will be repeated based on the PPT Population to confirm the results.

# 6 SAMPLE SIZE CONSIDERATION

The assumptions used to power this study are based on the Phase 2 study (SPR.18223) on the Non-Japanese population. Success rates based on IGA are assumed 23% (CD5789) and 15% (Vehicle). For a 90% power to detect a significant difference versus vehicle using a two-sided test at a type I error of 0.05, 504 subjects per arm are needed for analysis.

Based on the results from statum 1 in the phase 2 study (SPR18223), the mean difference between the active and vehicle is estimated at 3 inflammatory lesions and 6 non-inflammatory lesions. Standard deviation of changes in lesion counts, based on phase 2 and on large phases 3 trials from other projects are estimated at 12 for inflammatory lesions and 20 for non-inflammatory lesions. Using these as assumptions and a sample of 504 evaluable subjects per arm, power is 95% at least for both lesion types.

Galderma R&D RD.06.SPR.18252 Page 12 of 25

To compensate for drop-outs and non-evaluable subjects (estimated at 16%), a total of 1200 subjects are to be randomized into each treatment group in a 1:1 ratio stratified by center, with 600 subjects in each treatment group randomized.

The assumptions for truncal acne being the same as for facial acne in terms of efficacy, therefore it is estimated that the power for truncal acne is adequate.

## 7 STATISTICAL METHODS AND DATA CONSIDERATIONS

For statistical analyses purpose, baseline is defined as the last measurement prior to the first application of the study drug.

A type I error of 0.05 (two-sided test) will be used to declare statistical significance.

In general, no formal inferential analyses are planned for the baseline and safety data, and only summary statistics will be provided.

For the summary statistics, the categorical will be summarized by frequency and percentage for each response category (N, %); and the continuous will be summarized using means, medians, minimum, maximum, and standard deviations.

SAS version 9.3 or above will be used for all statistical analyses.

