11.4 Nodules and cysts count

Nodules and cysts, if present, will be recorded at each visit.

12/ STUDY DRUG DESCRIPTION

	Investigational Product	Comparator Product
Trade Name or Equivalent	N/A	N/A
Name of Drug Substance	N/A	Vehicle
Internal Code	CD5789	N/A
Pharmaceutical Form	Cream	Cream
Strength/ Concentration	50µg/g	N/A
Formula number	0219.0102	0219.0082P
▪ Packaging (type and size)	50 mL bottle with pump and overcap	50 mL bottle with pump and overcap
▪ Storage conditions	Store below 25°C (77°F), do not freeze or refrigerate	
▪ Location of Treated Area	Face: forehead, nose, chin and right and left cheeks	Face: forehead, nose, chin and right and left cheeks

	Investigational Product	Comparator Product
	Truncal region: right and left shoulders, right and left upper anterior chest, and right and left upper back; reachable to self-application by the subject.	Truncal region: right and left shoulders, right and left upper anterior chest, and right and left upper back; reachable to self-application by the subject.
▪ Route	Topical	Topical
▪ Dose Regimen	Once daily in the evening after washing the treated areas	Once daily in the evening after washing the treated areas
▪ Duration of administration	12 Weeks	12 Weeks

▪ N/A = Not Applicable

Schedule of assessments

	Screening Visit 1 (maximum 14 days+3 days prior to Baseline)	Baseline Visit	Week 1 Visit (±3 days)	Week 2 Visit (±3 days)	Week 4 Visit (±3 days)	Week 8 Visit (±3 days)	Week 12 Final/ET Visit ² (±5 days)
Informed Consent/ HIPAA (US only)/ PIPEDA (Canada only) and Assent Form/ Photo Consent (selected sites)	X						
Demographics	X	X ³					
Medical History	X	X ³					
Previous Therapies/Procedures	X						
Vital Signs/Physical Examination	X	X					X
Laboratory Safety Test (hematology, chemistry, Urine Analysis)	X						X
Urine Pregnancy Test ⁴	X	X ³			X	X	X
IGA (face)	X	X ³	X	X	X	X	X
PGA (trunk) ⁵	X	X ³	X ⁵	X ⁵	X ⁵	X ⁵	X
Acne Lesion Counting on the Face	X	X ³	X	X	X	X	X
Acne Lesion Counting on the Trunk ⁵	X	X ³	X ⁵	X ⁵	X ⁵	X ⁵	X
Local tolerability on treated areas		X	X	X	X	X	X
Photographs (Face and Trunk at selected centers) ⁶		X		X	X	X	X
Inclusion/Exclusion Criteria ³	X	X ³					
Randomization		X					
Adverse Event recording ⁷	X	X	X	X	X	X	X
Concomitant Therapies/Procedures ⁸		X	X	X	X	X	X
DLQI or CDLQI ⁹		X					X

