	Screening Visit 1 (maximum 14 days+3 days prior to Baseline)	Baseline Visit	Week 1 Visit (±3 days)	Week 2 Visit (±3 days)	Week 4 Visit (±3 days)	Week 8 Visit (±3 days)	Week 12 Final/ET Visit ² (±5 days)
Skin Oiliness Scale (SOS) Questionnaire ¹¹		X					X
Self-assessment of facial acne improvement							X
Study drug(s) Dispensing (D) and Accountability (A)		D			D/A	D/A	A
Moisturizer/cleanser Dispensing (D)		D ¹⁰					
Dosing calendar Dispensed (D) returned and reviewed (RR)		D	RR	RR	RR	RR	RR
Exit Form ¹¹							X

- (1) Baseline visit must be performed maximum 14 days after Screening with a time window of +3 days. For women of childbearing potential, there must be at least 14 days between Screening and Baseline visits (for UPT reason). No re-screening will be allowed.
- (2) Week 12 procedures will be performed earlier in case of study discontinuation.
- (3) Confirm information at Baseline
- (4) For subject of childbearing potential only: Urine Pregnancy Tests will be performed at Screening, Baseline, Week 4, Week 8, Week 12. For pre-menstrual subjects re-confirm pre-menses status at every visit and in case of status change collect information on contraceptive method and perform a UPT. For the ones who begin menses after the Screening visit, urine pregnancy tests will be performed at the visit where there was a change in status and according to the schedule for females of childbearing potential (Baseline, Week 4, 8, 12/ET). Additional UPTs may be performed at the investigator's discretion.
- (5) Subjects 9 to 11 years of age who did not meet the criteria for moderate truncal acne at Baseline: PGA will be evaluated after baseline to allow the investigators to decide to start the treatment on the trunk if the subject develops truncal acne during the study whatever the PGA grade. Local tolerability will be assessed. The Lesion counts will not be evaluated.
- (6) Photos are not mandatory; subjects will be able to participate in the study even if they refuse to participate in photo procedures.
- (7) Collection of Adverse Events will begin after signing of the informed consent/assent form.
- (8) Medication that continues after Screening visit should be recorded on the Concomitant Medication page of the eCRF. Medical or surgical procedures occurring after Screening visit should be recorded on the Procedures page of the eCRF

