#### 7.5.1.2 Treatment Duration

Treatment duration (day) is defined as "the date of the last application on face or the trunk, whichever is later, minus the date of the first application on face or the trunk, whichever is earlier, plus one".

Treatment duration will be summarized by descriptive statistics using the SAF population.

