## 7.7 Analysis visit definition

All efficacy variables and local tolerability variables will be summarized and analyzed by analysis visit. Analysis visit will be imputed according to the following algorithm to summarize the data by proper visit window interval. Study day is calculated as visit date minus the date of first application plus 1.

Table 4 Analysis Visit and Visit Window				
Analysis Visit	Analysis Visit Number in Derived Dataset	Target Study Day	Visit Window (Study Day)	
Baseline	1	1	[<=1]	
Week 1	2	8	[2-11]	
Week 2	3	15	[ 12 – 21 ]	
Week 4	4	29	[ 22 – 42 ]	
Week 8	5	57	[ 43 – 70 ]	
Week 12	6	85	>70	

If multiple measurements are taken in the same interval, the one closest to the target study day will be used for the analysis. If two measurements are taken with equal differences in timing compared with the target date, the nominal visit number (recorded on the CRF page) will used.

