#### 2.4. Subgroup Analysis

Subgroup analyses for IGA and PGA success rate at Week 12, absolute change from baseline for inflammatory and non-inflammatory lesion counts at Week 12 on the face and trunk, treatment-emergent adverse events by SOC and PT, and local tolerability parameters worsened from baseline on the face and trunk will include an analysis by:

- Age: 9-11 years, 12-17 years, and  $\geq 18$  years of age
- Gender: female and male
- Age and gender: female <25 years, male <25 years, female >=25 years, and male >=25 years
- Race: White, Black or African American, Asian, and Other
- Ethnicity: Hispanic or Latino and Not Hispanic or Latino
- Skin Phototype: I-III and IV-VI

In addition, a subgroup analysis for IGA and PGA success rate at Week 12, treatment-emergent adverse events by SOC and PT, and local tolerability parameters worsened from baseline on the face and trunk will be provided for the additional age categories of: <14 Years, 14-17 Years, and >=18 Years.

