#### 7.4. Local Tolerability

Local tolerability will be summarized by visit on the face and trunk separately. Summaries will present descriptive statistics of local tolerability scores when treated as a continuous measure, as well as counts and percentages of subjects with each score treated as categorical. Categorical summaries of scores that are worsened from baseline will also be presented.

Worsened from baseline is defined as having a local tolerability assessment at the summarized time point that is greater than the local tolerability assessment at baseline.

Subgroup analysis of local tolerability scores will be presented separately for the face and trunk. These summaries will treat the scores as categorical, and will present scores that have worsened from baseline for both the final and worst scores per subject.

Local tolerability scores will also be presented treating the score as dichotomous. Subjects will be summarized into two categories based on their score: "None (0)" or "Mild/Moderate/Severe (1-3)," and presented at Baseline, Final visit, and their Worst score.

Graphical assessment of local tolerability will be done on all subjects, not just those with a local tolerability assessment worsened from baseline. Subgroup analysis of local tolerability will not be graphed.

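### Trunk tolerability has no baseline tied to the first truncal application, so the worsened-from-baseline analysis is undefined or misaligned for 9-to-11-year-olds who start trunk treatment late

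*SAP*

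**What the plan says.** **Baseline and visit clock.** SAP section 7 states that "baseline is defined as the last measurement prior to the first application of the study drug". It names no body area. SAP section 7.7 covers local tolerability as well as efficacy: "Study day is calculated as visit date minus the date of first application plus 1". In its Table 4, Baseline is study day 1 or earlier and every later day falls in a post-baseline window. Neither section gives a separate date for the trunk. For treatment duration, SAP section 7.5.1.2 counts days "minus the date of the first application on face or the trunk, whichever is earlier, plus one".

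**Late trunk starters.** In the Protocol's Schedule of assessments, footnote 5 keeps the PGA going after Baseline in 9-to-11-year-olds without moderate truncal acne, "to allow the investigators to decide to start the treatment on the trunk if the subject develops truncal acne during the study". SAP section 3.2 says that if the investigator does so, "then the local tolerability scales (for trunk) will be completed and data will be evaluated in the safety analysis". SAP section 5.4 puts anyone with at least one truncal application in SAFT.

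**Analysis.** SAP section 4.2 lists change from baseline in trunk tolerability as a safety endpoint. SAP section 7.5.3 tabulates worsening by visit, at its worst and at the final assessment. Section 7.4 of the October 2017 document that clarifies the SAP defines worsening as a score "greater than the local tolerability assessment at baseline". Section 2.4 of that document lists "Age: 9-11 years, 12-17 years" among the subgroups for this analysis on face and trunk.

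**The concern.** For a child who starts with the face and adds the trunk later, the first application of study drug is facial. A trunk score recorded at the visit where trunk treatment is decided is the natural pre-treatment reference for the trunk. The plan's clock makes it a post-baseline value.

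The plan commits to evaluating these children's trunk data for safety and gives their age band its own tolerability subgroup. If the worsening flag cannot be derived for them, or is derived against the wrong time point, that table may omit irritation caused by truncal use or count skin changes that came before it.

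**Working it through.** The plan states no figure on this point, so there is none to reproduce. The check is a reading of the definitions, followed by a scale calculation on stated assumptions.

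**Step 1: is the anchor one date per subject?** The baseline sentence alone could be read area by area. SAP section 7.7 makes that hard to sustain: it names local tolerability, uses one date of first application and offers no trunk version. Section 7.1 of the October 2017 document separates treatment duration for face and trunk, but sets no trunk baseline or trunk visit window.

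**Step 2: follow one late starter.** Assume that trunk treatment is decided at the Week 4 visit, that visits fall on the target days of SAP Table 4, and that the first truncal application is that evening (dosing is in the evening).

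| Visit | Study day | Class in SAP 7.7 | Trunk when scored | Class on a trunk clock |
|---|---|---|---|---|
| Baseline | 1 | baseline | untreated | before trunk treatment |
| Week 1 | 8 | post-baseline | untreated | before trunk treatment |
| Week 2 | 15 | post-baseline | untreated | before trunk treatment |
| Week 4 | 29 | post-baseline | untreated | trunk baseline |
| Week 8 | 57 | post-baseline | treated | trunk day 57 − 29 + 1 = 29 |
| Week 12 | 85 | post-baseline | treated | trunk day 85 − 29 + 1 = 57 |

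Three of the five post-baseline visits come before any truncal exposure.

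**Step 3: is there a trunk score at Baseline?** The documents point both ways.
- Against: the schedule row reads "Local tolerability on treated areas", and SAP section 3.2 links the trunk scales to the decision to treat.
- For: that row is marked at Baseline and carries no footnote 5, unlike the trunk PGA and trunk lesion rows. Footnote 5 itself says, without condition, that tolerability is assessed. SAP section 3.2 also has face and trunk assessed separately.

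**Step 4: consequence in each case.**
- *Not scored at Baseline.* The Week 4 score cannot serve as baseline, so the flag at Weeks 4, 8 and 12 has no comparator. Laboratory shifts (SAP 7.5.4) and DLQI/C-DLQI (SAP 7.6) require both assessments; the tolerability sections have no such rule. The programmer would have to choose between dropping the child and counting the child as not worsened.
- *Scored at Baseline.* The flag can be computed, but any trunk scores at Weeks 1, 2 and 4 may enter the by-visit and worst-score tables as on-treatment. A rise from 0 to 1 at Week 2, on an untreated trunk, would count as worsening.

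**Step 5: scale (assumptions, not plan figures).** Let a share f of SAFT be late starters without a trunk baseline, kept in the denominator as not worsened. A true worsening rate p then reads p × (1 − f). Take p = 30% and, for scale, 600 per arm (the planned number randomized, SAP section 6).
- f = 0.5%: 600 × 0.005 = 3 per arm; 30% × 0.995 = 29.85%.
- f = 5%: 600 × 0.05 = 30 per arm; 30% × 0.95 = 28.5%.

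Within the 9-to-11 subgroup of SAFT, f could be anything from 0 to 1, so the reading could lie anywhere from 30% down to 0%. At f = 0.4, for illustration, it is 30% × 0.6 = 18%.

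**The case against.** The strongest reply has four parts.

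- **The baseline sentence names no area.** Where the SAP means the earlier of face and trunk, as for treatment duration, it says so. This shows that section 7 alone is ambiguous. It does not remove the single clock that section 7.7 applies to tolerability.
- **The trunk may well be scored at Baseline.** SAP section 3.2 says what happens if trunk treatment starts; it does not say that the trunk goes unscored otherwise. It also refers to protocol sections 7.2.1 to 7.2.5, which are not in the protocol text available. This stands. A reader might infer that late starters have no valid baseline at all, and the documents do not establish that. The misalignment remains in either case.
- **Irritation would still be visible.** A reader might infer that worsening on the trunk could not be detected. That goes too far. Section 7.4 of the October 2017 document, which overrides the SAP where they differ, also summarizes all trunk scores by visit, splits none from mild-to-severe at Baseline, final and worst, and graphs all subjects. Adverse events are recorded at every visit. This stands: only the worsened-from-baseline analysis is affected.
- **Few or no children may be involved.** SAP section 5 allows for SAFT being identical to SAF, children whose trunk treatment starts at Baseline are unaffected, and safety analyses are descriptive. This also stands and limits the weight of the point.

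A further objection is that a new baseline definition does not help a child with no trunk score before the first truncal application. That is fair, and a denominator rule is therefore needed as well.

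**Conclusion.** The point holds as a minor one. The plan's baseline and visit windows for local tolerability rest on a single date of first application, and the design lets some children start the trunk later. For them the worsened-from-baseline result on the trunk is either undefined, with no handling rule, or mixes visits before and after truncal treatment.

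On the assumptions in the working, the shift in the whole-SAFT table is at most 1.5 percentage points (30% read as 28.5%). Within the 9-to-11 subgroup it could be large or nil, because the documents do not give the number of late starters. Efficacy is untouched: under SAP section 5.2 these children are outside the trunk efficacy population.

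The conclusion rests on reading section 7 together with section 7.7. It does not depend on whether the trunk was scored at Baseline; that only decides which of the two faults occurs.

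**What to change.** For trunk tolerability only, add to SAP section 7 and to section 7.4 of the October 2017 document:

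1. Baseline is the last trunk score on or before the day of the first application to the trunk, and taken before that application.
2. Only later trunk scores count as on treatment, in the by-visit, final and worst-score tables.
3. SAFT subjects with no trunk baseline are left out of the worsening denominator, and their number is reported by treatment group.

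It would also help to state whether trunk tolerability is scored at Baseline in all 9-to-11-year-olds. The face definition stays as it is.

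The cost is a few sentences and one extra derivation; visits and treatment do not change. The definition is workable because SAP section 3.2 ties trunk scoring to the decision to treat and dosing is in the evening, so a score at the decision visit should precede the first truncal dose. The downside is that late starters' trunk scores no longer line up with time since the first facial application: in the example above, Week 12 becomes trunk day 57.
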